Statistical analysis	Our hypothesis is that 20% of biopsy-proven tumors will be detected on PET-hrMRI and not on standard MRI. If we assume that no biopsy proven tumors will only be detected on standard MRI, at alpha=0.05, n=40 provides a power of at least 90% when we account for 5 cases that will not be evaluable. The RP phase II study is a parallel study arm using PSMA-PET imaging for intraprostatic cancer detection, but using radical prostatectomy pathology as the gold standard. The radical prostatectomy pilot arm will allow us to compensate for limitations and describe this data in parallel with the HIFU analysis.		

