#### 6.0 STATISTICAL ANALYSIS

# 6.1 HIFU Phase II Study

Our preliminary data suggests that up to 60% of tumors invisible to standard mpMRI are detected on hrMRI in an active surveillance population. It is unclear how many additional lesions will be identified on PSMA PET-MRI. Since all areas of concern will be biopsied and only biopsy-proven tumors will be treated with HIFU, the morbidity of the surgical intervention is minimized and its potential to achieve cure is maximized.

Power Assessment: The main hypothesis to be tested is whether the sensitivity of PSMA PET-hrMRI is greater than mpMRI alone in 20% considering the prostate divided in 6 sections for each patient. The power is evaluated using 1000 simulations based on the McNemar's type test proposed by Yang et al. (17,2010). Data is generated based on four correlations: r1: between lesions evaluated by PSMA PET-hrMRI for the same patient, r2: between lesions evaluated by mpMRI for the same patient, r3: between evaluations PSMA PET-hrMRI and mpMRI for the same lesion and r4: between evaluations PSMA PET-hrMRI and mpMRI for the different lesions at the same patient. Based on preliminary data, we estimated mpMRI sensitivity of 42%, (r1, r2, r3, r4) = (-0.249, -0.119, 0.714, -0.172) using Spearman correlation, average number of lesions of 2.5 per patient and prevalence of patients with at least one positive biopsy section equal to 82%. The results are presented in Table 1.

**Table 1.** Power for McNemar test proposed by Yang et al. (2010) to detect a difference of 20% between sensitivities of the combination (PET-hrMRI or mpMRI) and mpMRI

Total Sample # Patients with at least one positive biopsy
Size section Power

20	16	70.2
25	21	81.5
30	25	88.9
35	29	93.1
40	33	95.5

The minimum sample size to reach at least 85% of power is 30 patients with complete imaging data. Patients with incomplete imaging data will be replaced.

Statistical Analysis: Sensitivities will be compared using McNemar's type test proposed by Yang et al. (17,2010). for cluster matched binary data. In addition, the 95% confidence interval for difference between sensitivities will be calculated as proposed by Yang et al. (18,2012).

Secondary Endpoints: Negative biopsy rate within treatment zones on standard 12-core biopsy 6 months following HIFU therapy; rate of high grade cancer in the untreated lobe.

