# 6.2 Radical Prostatectomy Phase II Study

Our previously conducted pilot study investigating the impact of fluciclovine PET imaging on improving sensitivity of prostate cancer detection (identical to this study but using fluciclovine tracer instead of PSMA) was criticized due to lack of a gold standard based on radical prostatectomy (outcome was based on biopsy only). Since the HIFU arm in this PSMA PET study has a biopsy-only gold standard, we elected to include a parallel study arm using PSMA-PET imaging for intraprostatic cancer detection but using radical prostatectomy pathology as the gold standard. While there are historical references for sensitivity of PSMA-PET for intraprostatic cancer detection, they are not ideal to be used as a reference for our study since: they are few in number and may not provide generalizable estimates; the analysis to date has only been done on a per-patient (rather than a per-lesion) basis; and there is variation in reading of mpMRI by center/radiologist. The described parallel radical prostatectomy pilot arm will allow us to compensate for these limitations and describe this data in parallel with our HIFU analysis.

Power Assessment: The main hypothesis to be tested is whether the sensitivity of PSMA PET-hrMRI is 20% greater than mpMRI alone on a per lesion basis. It is expected 6 lesions in average per patient. Therefore, the power considerations are the same as presented for the HIFU cohort as displayed on Table 1.

**Table 1.** Power for McNemar test proposed by Yang et al. (2010) to detect a difference of 20% between sensitivities of the combination (PET-hrMRI or mpMRI) and mpMRI

Total Sample Size	# Patients with at least one positive biopsy section	Power
20	16	70.2
25	21	81.5
30	25	88.9
35	29	93.1
40	33	95.5

Statistical Analysis: Sensitivities will be compared using McNemar's type test proposed by Yang et al. (17,2010). for cluster matched binary data. In addition, the 95% confidence interval for difference between sensitivities will be calculated as proposed by Yang et al. (18,2012).

Secondary Endpoints: Specificity of imaging for detecting all tumors on prostatectomy

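### Table 1's power is labelled for the combined reading but belongs to PET-hrMRI alone versus mpMRI, and the Study Summary still quotes n=40

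*Combined protocol and SAP*

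**What the plan says.** The power paragraph of Section 6.1 gives the main hypothesis as "whether the sensitivity of PSMA PET-hrMRI is greater than mpMRI alone in 20" per cent. It defines the correlations for that pair of readings, for example "r3: between evaluations PSMA PET-hrMRI and mpMRI for the same lesion", and lists the inputs as "mpMRI sensitivity of 42%, (r1, r2, r3, r4) = (-0.249, -0.119, 0.714, -0.172) using Spearman correlation". It adds a mean of 2.5 lesions per patient and 82% of patients with at least one positive section.

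Table 1, presented as the result, is titled as power "to detect a difference of 20% between sensitivities of the combination (PET-hrMRI or mpMRI) and mpMRI". It shows 70.2, 81.5, 88.9, 93.1 and 95.5% for 20, 25, 30, 35 and 40 patients. The section concludes: "The minimum sample size to reach at least 85% of power is 30 patients with complete imaging data".

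Section 6.2 asks "whether the sensitivity of PSMA PET-hrMRI is 20% greater than mpMRI alone on a per lesion basis" and reprints the same table under the same title.

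The Study Summary lists 30 HIFU subjects, but its statistical analysis entry says "n=40 provides a power of at least 90% when we account for 5 cases that will not be evaluable". It reaches that figure with this premise: "If we assume that no biopsy proven tumors will only be detected on standard MRI".

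**The concern.** The hypothesis sentence and the table title name different comparisons. If the new test is PET-hrMRI alone, some lesions may be seen by mpMRI only, and these count against it. If the new test is positive whenever PET-hrMRI or mpMRI is positive, that cell is empty by construction and all discordance runs one way. The same 20-point gain then carries much less variance and much more power.

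The endpoint in Section 3.3 (additional cancers found by hrMRI and/or PET) does not say whether mpMRI is part of the new test. A reader therefore cannot be sure which test the 88.9% supports, and the primary contrast could be settled after the results are known. The 20 points also do not carry over from one contrast to the other. Finally, the Summary quotes a sample size and power that the current design does not have.

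**Working it through.** **Inputs from Section 6.1.** mpMRI sensitivity is 0.42 and the gain is 0.20, so the new test is at 0.62. The correlations are r1 = −0.249, r2 = −0.119, r3 = 0.714 and r4 = −0.172. There are 2.5 lesions per positive patient and 16/21/25/29/33 positive patients. Alpha 0.05 comes from the Study Summary. Assumed: a two-sided test, 2.5 as the mean among positive patients, and the lesion-count distribution.

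**Step 1: is r3 feasible between yes/no readings?** The largest correlation of two binary readings at 42% and 62% is √[(0.42 × 0.38)/(0.62 × 0.58)] = √(0.1596/0.3596) = 0.666. On that scale a Spearman coefficient is the ordinary binary correlation, so 0.714 cannot occur.

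**Step 2: reproduce Table 1 for PET-hrMRI alone.** Put r3 = 0.714 on a latent-normal scale:

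- both positive 0.373; PET-hrMRI only 0.62 − 0.373 = 0.247; mpMRI only 0.42 − 0.373 = 0.047
- implied binary correlation 0.469
- covariance of the reading differences between two lesions in one patient, from r1, r2 and r4: −0.0025

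With L = 2.5 × positive patients and d = 0.20, power ≈ Φ(d√(L/V) − 1.96), where V = discordance − d² + 1.5 × covariance = 0.2943 − 0.04 − 0.0037 = 0.2506. At 25 positive patients, L = 62.5 and power is Φ(0.20 × √(62.5/0.2506) − 1.96) = 88.5%.

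The exact form of the cited test is not in the documents, so two clustered variance forms were also simulated (10,000 trials per cell, three lesion-count distributions).

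| Positive patients | 16 | 21 | 25 | 29 | 33 |
|---|---|---|---|---|---|
| Table 1 (%) | 70.2 | 81.5 | 88.9 | 93.1 | 95.5 |
| Normal approximation (%) | 71.5 | 82.5 | 88.5 | 92.5 | 95.2 |
| Simulation, centred variance (%) | 72–73 | 83–84 | 89 | 93 | 95–96 |
| Simulation, null variance (%) | 62–63 | 78–79 | 86–87 | 91–92 | 94–95 |

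The approximation is within 2 points of every row. One-sided testing gives 93.5% at 25, and setting all correlations to zero gives 62.7%. Neither matches 88.9%.

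**Step 3: the combination at 62% against mpMRI at 42%.** The mpMRI-only cell is zero and discordance is 0.20. Treating lesions as independent, V = 0.20 − 0.04 = 0.16.

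- 25 positive patients: Φ(0.20 × √(62.5/0.16) − 1.96) = Φ(1.99) = 97.7%. Clustered simulation gives 99.4–99.9%, and an exact binomial test on 62 lesions gives 99.1%.
- 16 positive patients: 88.5% by approximation, 88–96% by clustered simulation, and 83.9% by exact binomial on 40 lesions.
- In simulation, 85% is first passed at 13 to 16 positive patients. That is 13/0.82 = 15.9 to 16/0.82 = 19.5, or about 16 to 20 enrolled.

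**Step 4: are the two effects interchangeable?** In the latent model, PET-hrMRI at 62% puts the combination at 0.62 + 0.047 = 66.7%, a gain of 24.7 points. Conversely, a combination at 62% puts PET-hrMRI alone at 55.2%, a gain of 13.2 points. Pairing the title's effect with the hypothesis sentence's test then gives 51–58% power at 25 positive patients (56% by the approximation).

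**Step 5: the Summary.** 40 − 5 = 35, and Table 1 shows 93.1% at 35, so at least 90% fits 40 enrolled. At the current 30, Table 1 shows 88.9%. The Summary's premise of no mpMRI-only tumours is also not the model that reproduces Table 1, which has 4.7% of lesions in that cell.

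**The case against.** The best defence is that this is a labelling slip with little consequence. The hypothesis sentence, the correlation definitions and the reproduced figures all point to PET-hrMRI alone, so only the title is out of place. Under the Summary's premise that nothing is seen only on standard MRI, PET-hrMRI and the combination are the same reading. The 4.7% cell comes from a latent model that the protocol does not state, and one of the two variance forms misses Table 1 at the small sizes. The 0.666 ceiling applies at the planning values: if PET-hrMRI sensitivity in the preliminary data was between 42% and about 58.7%, a binary correlation of 0.714 could have been observed there.

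Much of this stands. The direction is conservative for the combination, and the modelled figures depend on unstated choices. The claim that 20 patients already reach 85% for the combination holds for the clustered tests but not for the exact binomial, which is not the planned analysis. The 51–58% case arises only if the title's effect is paired with the other test.

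It does not remove the mismatch. If the Summary's premise is used to merge the two contrasts, the mpMRI-only cell is zero and 88.9% is not the power. If the premise is dropped, the contrasts differ. Wherever the correlations were estimated, they cannot be imposed on yes/no readings at 42% and 62%.

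**Conclusion.** The plan is wrong as written. Table 1's figures fit PET-hrMRI alone against mpMRI and not the combination in its title. For the combination at a 20-point gain, power at 30 enrolled is 97.7–99.9% depending on method, against the 88.9% shown, and 30 is not its minimum. Naming Spearman does not say whether the correlations act on latent variables or on the yes/no readings, and the second is infeasible. The Summary's n=40 with at least 90% is out of date against 30 patients and 88.9%.

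These results assume a two-sided 5% test and 2.5 lesions on average among positive patients. If 2.5 is the mean over all patients, PET-hrMRI alone has 91.7–93.8% power at 30 enrolled. Enrolment is not shown to be too small: with 20 points on the contrast actually tested, 30 patients exceed 85% for either one. The point should be fixed because it leaves the primary contrast and its power unclear in both arms.

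**What to change.** Choose one primary contrast and use it in the Section 6.1 hypothesis, the Table 1 title, Section 6.2 and the Study Summary.

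- If PET-hrMRI alone is kept, correct the table title and state the scale of r1–r4. If the original simulation did not use a latent scale, re-run it with a binary correlation no higher than 0.666.
- If the combination is chosen, re-run Table 1 with the mpMRI-only cell set to zero and revise the minimum sample size statement.
- In either case, state sidedness, the lesion-count distribution and the variance form of the test.
- Replace the Summary's n=40 power sentence with the power at n=30. Keep alpha = 0.05, which is stated only there, and align the premise about tumours seen only on standard MRI with the chosen model.

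The cost is at most one re-run simulation, plus wording in three places. Enrolment and procedures do not change.

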We herein propose a prospective trial to evaluate the effectiveness of F18-PSMA PET-hrMRI versus standard mpMRI at identifying prostate cancer targets for HIFU therapy. Patients with clinically localized, unilateral high grade prostate cancer (Gleason score 7-10 prostate cancer localized to one lobe on prior biopsies) OR at high risk for having unrecognized high grade prostate cancer (overall Gleason score 6 with ≥ half of systematic biopsy cores positive and ≥ 50% of core involvement in at least one core), interested in HIFU would receive both a standard mpMRI and F18-PSMA PET-hrMRI. They would then undergo a mapping biopsy using a standard sextant template plus MRI/US-fusion targeted biopsy of any suspicious lesion on mpMRI or PET-hrMRI. The primary endpoint would assess the number of biopsy-proven cancers that mpMRI would have missed compared with PET-hrMRI. Following our tumor mapping study, patients with high grade disease (i.e. Gleason grade 4 or 5) in one lobe undergo hemigland or focal HIFU of that lobe. At 6 months, patients would undergo repeat prostate biopsy to assess the negative biopsy rate in the treated region and absence of Gleason grade 4 or 5 in the untreated region as secondary endpoints.

Tumors invisible on MRI tend to be small, low-grade tumors that do not require treatment. However, it may be important to identify these tumors for future surveillance. An important limitation of this phase II study is that it will not be able to define the sensitive of imaging for these low-grade tumors. Therefore, a pilot study is included in which patients scheduled to undergo radical prostatectomy will have a preoperative PET-hrMRI. The prostatectomy pathology will be the reference standard. Since the true location of all tumors will be known, both the sensitivity and specificity of PSMA-PET MRI can be determined

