# 2.2 HIFU: Historical Background and FDA Approval

High-Intensity Focused Ultrasound (HIFU) is a noninvasive therapy that precisely delivers ablative ultrasonic energy to deep tissues through skin and mucosa, allowing for transrectal focal ablation of prostate cancers. While the mainstays of therapy for clinically localized prostate cancer induce significant morbidity such as urinary incontinence, erectile dysfunction, and bowel dysfunction due to bystander effects of whole-gland treatment, HIFU permits focal destruction of prostate cancers by ablating either half of the prostate gland or only the tumor itself; these approaches have the potential to minimize morbidities associated with whole-gland treatment and thereby maximize quality of life. HIFU treatment (primarily hemigland and whole-gland) has been used extensively over the last fifteen years in Europe, Canada, and Mexico, and there are numerous articles describing its safety and effectiveness for this application in the Urology literature.

While HIFU therapy has a long track record abroad, it has only recently been approved for prostate ablation in the US. In October 2015, the FDA gave de novo clearance to the Sonablate 450 HIFU platform (manufactured by SonaCare Medical) for the ablation of prostate tissue, making it the first to be approved for this indication in the US. In November 2015, the Ablatherm HIFU platform (manufactured by EDAP TM SA) was given 510(k) clearance for the same indication. While the approvals for these devices do not specifically mention application to prostate cancer, academic and industry leaders are hailing this technology as a major advance for focal prostate therapy, hinting that this technology can avoid the morbidities of surgery for prostate cancer. Local academic centers have already begun to use and market this technology.

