# 2.8 Combining MR/US-Fusion, hrMRI, and PET-MRI with HIFU for Focal Treatment of Prostate Cancer

Because the oncological effectiveness of HIFU depends on robust mapping and targeting of lesions within the prostate, improved detection of lesions using hrMRI and/or PET-MRI could provide a significant advantage in HIFU cancer control outcomes. Patients who are eligible for hemigland and focal HIFU absolutely depend on imaging for treatment planning; for example, in a patient with an index lesion of the right side of the prostate only, if imaging fails to detect a small focus of prostate cancer present on the left, hemigland HIFU (only treating the right side of the prostate) will not be effective at eradicating the entire bulk of his disease. It is even more important to accurately identify all prostate cancers when mapping for true focal therapy, since only identified lesions are ablated. We have previously shown that hrMRI detects up to 60% of tumors within the prostate not seen on mpMRI, and PET-MRI techniques may be able to improve the accuracy of this detection. Even if lesions that are ignored by mpMRI but detected on PET-hrMRI are indolent, long-term growth of these lesions may certainly affect cancer control outcomes over time and require costly and morbid retreatment. We believe that improved imaging at the outset of focal therapy would provide more comprehensive eradication of cancer burden from the start, resulting in improved long-term outcomes.

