#### 3.0 STUDY DESIGN:

#### 3.1 Overview

This prospective trial will evaluate the effectiveness of F18-PSMA PET-hrMRI versus standard mpMRI at identifying prostate cancer targets for HIFU therapy. Patients with clinically localized, Gleason score 7-10 prostate cancer localized to one lobe on prior biopsies or overall Gleason score 6 with ≥ half of systematic biopsy cores positive and ≥ 50% of core involvement in at least one core, interested in HIFU would receive both a standard mpMRI and F18-PSMA PET-hrMRI. They would then undergo a mapping biopsy using a standard sextant template plus MR/US-fusion targeted biopsy of any lesions with PI-RADS scores ≥3 on hrMRI or 18F-PSMA PET positivity. The primary endpoint of the Phase II study would assess the number of biopsy-proven cancers that mpMRI would have missed compared with hrMRI and/or F18-PSMA PET. Following our tumor mapping study, patients with high grade disease (i.e. Gleason grade 4 or 5) in one lobe undergo hemigland or focal HIFU of that lobe. At 6 months, patients would undergo repeat mpMRI and prostate biopsy (MR/US-fusion biopsy plus standard sextant biopsy) to assess the negative biopsy rate in the treated region and absence of Gleason grade 4 or 5 in the untreated region which will be the secondary endpoint of the Phase II study.

As the gold standard for evaluation of sensitivity and specificity of any imaging test is the pathologic analysis of the whole prostatic gland obtained at prostatectomy (as the biopsy is subject to error sampling), a concurrent pilot study will enroll patients scheduled to undergo prostatectomy with the primary endpoint to define sensitivity of PET-hrMRI versus mpMRI compared against the prostatectomy pathology and with the secondary endpoint define specificity of hrMRI, F18-PSMA PET and mpMRI for detecting all tumors and metastasis at 6 months follow up.

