## HIFU Therapy and Follow Up Schedule

Patients who are eligible for HIFU will receive hemigland or focal HIFU per standard-of-care. All subjects will receive repeat mpMRI and MR/US-guided biopsy of all positive sites + systematic 12-core prostate biopsy at 6 months (or as clinically indicated). As an exploratory analysis, remnant formalin-fixed paraffin embedded tumor tissue will be requested for RNAseg transcriptome analysis of lesions that are positive on biopsy.

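### The HIFU secondary endpoint is defined in three non-equivalent ways, and the Section 6.1 version can leave the untreated part of the treated lobe out of both of its outcomes after focal HIFU

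*Combined protocol and SAP*

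**What the plan says.** The post-HIFU endpoint appears in three forms.

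- **Section 3.3 and the Study Summary:** one rate, the proportion with a negative standard 12-core biopsy at 6 months. No zone, lobe or grade is mentioned.
- **Section 1.0 and Section 3.1:** two parts, the "negative biopsy rate in the treated region and absence of Gleason grade 4 or 5 in the untreated region".
- **Section 6.1, Secondary Endpoints:** two rates, "Negative biopsy rate within treatment zones on standard 12-core biopsy 6 months following HIFU therapy; rate of high grade cancer in the untreated lobe".

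Two extents of ablation are allowed. Section 3.1 says that "patients with high grade disease (i.e. Gleason grade 4 or 5) in one lobe undergo hemigland or focal HIFU of that lobe", and the HIFU Therapy and Follow Up Schedule repeats the choice: "Patients who are eligible for HIFU will receive hemigland or focal HIFU per standard-of-care". Section 2.2 describes HIFU as "ablating either half of the prostate gland or only the tumor itself". Section 2.8 says that complete mapping matters even more for true focal therapy, "since only identified lesions are ablated".

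At 6 months the schedule calls for targeted biopsy of positive sites plus a systematic 12-core biopsy. Patients with high-grade disease in both lobes are left out of the secondary endpoints (Eligibility for HIFU).

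**The concern.** The units in Section 6.1 do not match each other: one outcome is tied to a zone and the other to a lobe. A zone and the opposite lobe make up the whole gland only when the zone is itself a lobe. When only the tumour is ablated, tissue remains on the treated side that neither unit names.

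That tissue bears on the trial's rationale. Section 2.8 argues that lesions missed at mapping undermine focal treatment, and a lesion left on the treated side is one direct form of that. If Section 6.1 is followed literally, a focally treated man with Gleason grade 4 cancer in the same lobe but outside the ablated tissue is negative on the first outcome and absent from the second.

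The wider difficulty is that the same patient can be a failure or not depending on which section the analyst follows. Unless one definition is fixed beforehand, the choice could be made after the results are known.

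**Working it through.** The plan gives no target, test or power for this endpoint, so there is no figure to reproduce. The check is whether the units in each definition cover the gland, and how each definition classifies a given biopsy finding.

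**Step 1. Coverage under Section 6.1, reading the treatment zone as ablated tissue.**

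- Hemigland: ablated tissue (one lobe) + untreated lobe = whole gland. Nothing is left over.
- Focal: ablated tissue (part of one lobe) + untreated lobe = whole gland minus the unablated part of the treated lobe.

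**Step 2. Coverage under the other definitions.**

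- Sections 1.0 and 3.1: treated region + untreated region = whole gland for either extent of ablation, with only Gleason grade 4 or 5 counting in the untreated region.
- Section 3.3 and the Study Summary: the whole 12-core template, with cancer of any grade counting.

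**Step 3. Classification of 6-month findings**, each taken as the only cancer found and as sampled by a systematic core.

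| Cancer found in | 3.3 / Summary | 1.0 / 3.1 | 6.1 |
|---|---|---|---|
| Ablated tissue, any grade | failure | failure | failure |
| Opposite lobe, grade 4 or 5 | failure | failure | counted as high grade |
| Opposite lobe, lower grade | failure | not counted | not counted |
| Treated lobe outside ablated tissue, grade 4 or 5 (focal only) | failure | failure | **not counted** |
| Treated lobe outside ablated tissue, lower grade (focal only) | failure | not counted | not counted |

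Sections 3.1 and 6.1 part in the fourth row. Section 3.3 differs from both others in the third and fifth rows. The third row is not hypothetical: Section 3.4.1 admits men with low-grade cancer in the opposite lobe, and under Section 3.3 such cancer would make the 6-month biopsy a failure although it was not treated.

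**Step 4. Size.** Let N be the number treated with HIFU and counted for the secondary endpoints, f the share treated focally, and q the proportion of focal patients whose only countable cancer is high grade and in the unablated part of the treated lobe. The number that Section 6.1 leaves uncounted is

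uncounted patients = N × f × q.

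The documents give none of the three. The planned HIFU cohort is 30, and exclusion of bilateral high-grade disease lowers N. If f = 0 the result is 0. The only firm statement of scale is per patient: if N is at most 30, each uncounted man is worth at least 1/30 = 3.3 percentage points of any rate taken over all treated men.

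**The case against.** The strongest reply is that *treatment zones* may mean the whole treated lobe. The term is undefined, Section 3.1 speaks of HIFU of that lobe, and Section 6.1 pairs the zone with the untreated lobe. On that reading the gap closes. This reply stands as a possibility. It is the less natural reading, because Section 6.1 itself says that HIFU is applied only to tumours proven on biopsy, and because it uses two different words for its two units. If the lobe is meant, the text should say so, and Section 6.1 would then still differ from 3.1, since cancer of any grade in the unablated part of the lobe would count as failure.

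A second reply is that other sections already count this tissue. That is correct. A reader might infer that the trial has no endpoint that would register high-grade cancer beside the ablation zone. The documents do not support that: the abstract and Section 3.1 capture it, and so does the unrestricted rate in Section 3.3 and the Study Summary. The tissue is also sampled at 6 months. The fault is one of definition, not of data collection.

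A reader might also be tempted to put percentage points on the overstatement. Any such figure needs an assumed focal share and an assumed rate of cancer outside the zone, and would refer to a combined success rate that Section 6.1 does not define; it lists two separate rates. Nor is there ground to infer that the statistical section deliberately swapped region for lobe: the Summary of Changes records endpoint clarifications but shows no such substitution.

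**Conclusion.** The point holds in a limited form. The HIFU secondary endpoint has three definitions that classify some patients differently. On the natural reading of an undefined term, the one in the statistical section omits high-grade cancer in the unablated part of the treated lobe after focal HIFU. The omission needs two conditions: that the treatment zone means ablated tissue, and that some patients have focal treatment. If either fails, the gap is nil, but the three definitions still disagree.

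The size is unknown and cannot be obtained from the documents. The endpoint is secondary, with no hypothesis, threshold or power attached. The comparison of sensitivities and Table 1 are untouched. It is worth correcting because the statistical section, followed as written, would depart from the endpoint stated in Section 3.1, and the correction is cheap.

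**What to change.** 1. In Section 6.1, define the treatment zone as the ablated tissue.
2. In Section 6.1, replace the untreated lobe by the untreated region, meaning all tissue outside the ablation zone, including the untreated part of the treated lobe. This is consistent with Section 3.1.
3. Reconcile Section 3.3 and the Study Summary by naming these two outcomes there and also reporting the whole-template negative 12-core rate. The wider region in item 2 still counts only high-grade cancer; the whole-template rate picks up lower-grade cancer outside the zone. It should stand beside the two outcomes and not replace them, because it also counts low-grade disease in the opposite lobe that the protocol allows at entry.
4. Report all three for focal and hemigland patients separately, as counts with denominators.

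The cost is a few phrases, some table rows, and the assignment of each 6-month core to a location relative to the ablation zone. The documents do not say that core locations are recorded, although both present Section 6.1 outcomes already require this. No biopsy or visit is added. The reported high-grade rate may be less favourable.
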